8.5.2 Treatment compliance

All study procedures are to be performed under supervision at the study site, and thus, no separate procedures will be used to monitor subject compliance.

8.6 Efficacy analyses

8.6.1 Analysis methods

The analyses of the primary and secondary outcome measures will be based on different statistical tests such as Cochran-Mantel-Haenszel test, Pearson Chi-Square test, Wilcoxon Rank Sum test and Fisher's exact test, if appropriate. Details for each efficacy endpoint will be provided in the following sections. Subgroup analyses will be described in section 8.8.

8.6.1.1 Multiplicity

The testing of the primary and the five key secondary efficacy endpoints will be performed with appropriate multiplicity control based on the FAS population. The results of each test result will only be considered confirmative if the previous test in the order showed a confirmatory result at a one-sided significance level of 0.025. If the one-sided p-value is larger than 0.025 for any of the tests, the results of the subsequent tests will only be considered exploratory, and not confirmatory. The application of this hierarchical approach keeps the global significance level to 0.025 one-sided and requires no further adjustment of the significance level.

The following order of tests will be applied:

- Primary endpoint (composite endpoint)
- Key secondary endpoint 1 (composite endpoint)
- Key secondary endpoint 2 (composite endpoint)

Statistical Analysis Plan (SAP)

- Key secondary endpoint 3
 - 3.1: The investigator's in-clinic assessments
 - 3.2: The subject's in-clinic assessments
- Key secondary endpoint 4 (composite endpoint)
- Key secondary endpoint 5
 - 5.1: The modified Skindex-16 (GL-QoL) Emotional domain
 - 5.2: The modified Skindex-16 (GL-QoL) Functioning domain
 - 5.3: The modified Skindex-16 (GL-QoL) Overall score
 - 5.4: The FACE-Q Appraisal of Lines Between Eyebrows scale
 - 5.5: The FACE-Q Age Appraisal VAS score

All other analyses (e.g., additional analyses of the primary and the five key secondary efficacy endpoints using other analysis populations or other statistical methods, analyses of additional secondary endpoints) will only be considered exploratory.

8.6.1.2 Treatment by center interaction analysis (multi-center study)

Treatment-by-center interaction will be tested using the Breslow-Day test for homogeneity of the odds ratios for the primary efficacy endpoint.

8.6.2 Analysis of primary efficacy endpoint(s)

Primary Analysis:

The proportion of subjects (responders) meeting the primary endpoint with a FWS score of 0 or 1 and an improvement ≥ 2 points in FWS score (at maximum frown) at week 4 visit relative to baseline, based on both the investigator and the subject in-clinic assessments will be analyzed using the Cochran-Mantel-Haenszel test with stratification variable site using a significance level (α) of 0.025. Small sites with less than 3 placebo subjects will be combined. The null hypothesis H_0 given below will be tested against the alternative hypothesis H_1 :

$$H_0: p_{BoNT/A-DP} \leq p_{Placebo}$$

$$H_1: p_{BoNT/A-DP} > p_{Placebo}$$

The Cochran-Mantel-Haenszel test will be applied by the SAS procedure Proc Freq using the General Association Statistic. The one-sided p-value will be derived by halving the two-sided p-value delivered by the SAS procedure. Superiority of BoNT/A-DP over placebo will only be concluded if, besides statistical significance (one-sided p-value

Statistical Analysis Plan (SAP)

≤ 0.025), the proportion of responders in the BoNT/A-DP treatment group is higher than for the placebo treatment group.

The FAS will serve as the primary analysis set.

Subjects with missing investigator or subject in-clinic assessments with the FWS at baseline or visit week 4 will be assigned as being non-responders.

Additional Exploratory Analyses on the Primary Endpoint Variable:

Further analyses on the primary endpoint variable are exploratory. A one-sided Pearson χ^2 -test will be applied. Two-sided CI of 95% for the responder rates in the BoNT/A-DP and the placebo treatment groups will be calculated using Wilson scores. As a sensitivity analysis for the primary endpoint, a tipping point analysis will be performed. Each missing value will be assigned to either a response or non-response, so that all possible combinations of replacing one or more missing values within each treatment group will be analyzed. P-values will be calculated for each combination and graphically displayed using a scatter plot.

The CIs will also be calculated for the additional analyses as listed in the following:

- The primary endpoint measure using the observed values only, i.e. missing investigator or the subject in-clinic assessments with the FWS at baseline or week 4 visit will be excluded from analysis but not assigned as being non-responders. This analysis will be performed for the FAS, MFAS and PP populations.
- The primary endpoint measure using the MFAS and the PP.
- The primary endpoint measure applying the LOCF for week 4 visit. This analysis will be done for FAS, MFAS and PP populations.

8.6.3 Analysis of secondary efficacy endpoint(s)

The following order of tests will be defined for the analysis of the key secondary endpoints:

- Primary endpoint (composite endpoint)
- Key secondary endpoint 1 (composite endpoint)
- Key secondary endpoint 2 (composite endpoint)
- Key secondary endpoint 3
 - 3.1: The investigator's in-clinic assessments
 - 3.2: The subject's in-clinic assessments
- Key secondary endpoint 4 (composite endpoint)

Statistical Analysis Plan (SAP)

- Key secondary endpoint 5
 - 5.1: The modified Skindex-16 (GL-QoL) Emotional domain
 - 5.2: The modified Skindex-16 (GL-QoL) Functioning domain
 - 5.3: The modified Skindex-16 (GL-QoL) Overall score
 - 5.4: The FACE-Q Appraisal of Lines Between Eyebrows scale
 - 5.5: The FACE-Q Age Appraisal VAS score

For key secondary endpoints 2 – 4, the p-value to be considered within the hierarchical testing procedure is the one resulting from the Cochran-Mantel-Haenszel test as described for the primary efficacy endpoint in the first paragraph entitled “Primary Analysis” of section 8.6.2.

Analysis of key secondary endpoint 1: The percentage of responders at maximum frown (as defined above for the primary efficacy endpoint) at week 12 (after the first treatment with BoNT/A-DP or placebo).

The same analyses, inclusive the additional exploratory analyses, as described for the primary endpoint will be conducted.

Analysis of key secondary endpoint 2: The percentage of responders at maximum frown (as defined above for the primary efficacy endpoint) at week 16 (after the first treatment).

The analysis of the week 16 visit will be conducted on observed values only, i.e. missing investigator or the subject in-clinic assessments with the FWS at baseline or week 16 visit will be excluded from analysis but not assigned as being non-responders. Subjects who were re-treated before visit week 16 are considered to be non-responders.

In addition, the same analyses, inclusive the additional exploratory analyses, as described for the primary endpoint will be conducted as exploratory analyses. Subjects who were re-treated before visit week 16 are considered to be non-responders in all these analyses.

Analysis of key secondary endpoint 3: The proportion of subjects with a > 1 point reduction in FWS score at rest at week 4 in the first treatment cycle, based separately on the investigator and the subject in-clinic assessments

In general, the same statistical analyses, inclusive the additional exploratory analyses as described for the primary endpoint, will be conducted.

The analysis using the investigator’s in-clinic assessment will be conducted first with respect to the hierarchical order of key secondary endpoints, with the analysis using the subject’s in-clinic assessment second.

Statistical Analysis Plan (SAP)

All analyses (inclusive the additional exploratory analyses) on the investigator's in-clinic assessment will be conducted only for subjects who have an investigator's in-clinic assessment of a FWS score at rest > 1 at baseline. This will similarly be applied for the analyses of the subject's in-clinic assessment.

For the primary analysis (to be considered within the hierarchical testing procedure), subjects with missing investigator in-clinic assessments of FWS score at rest at baseline or week 4 visit will be assigned as being non-responders for this endpoint. This will similarly be applied for the subject's in-clinic assessment within the primary analysis.

As a consequence, the primary analysis will lead to exactly the same results as the LOCF analysis and thus the LOCF analysis will be skipped.

Analysis of key secondary endpoint 4: The percentage of responders at maximum frown (as defined above for the primary efficacy endpoint) at week 20 or later (after the first treatment).

The analysis of visit week 20 will be conducted on observed values only, i.e. missing investigator or the subject in-clinic assessments on FWS at baseline or visit week 20 will be excluded from the analysis but not assigned as being non-responders. Subjects who were re-treated before visit week 20 are considered to be non-responders.

In addition, the same analyses, inclusive the additional exploratory analyses as described for the primary endpoint, will be conducted as exploratory analyses (for subgroups also).

Analyses of other visits after first treatment but before re-treatment up to week 48 are exploratory only based on the FAS using descriptive statistics only. Subjects with re-treatment before the respective visit will be excluded from the analysis. Additional exploratory analyses, as described for the primary endpoint, will not be conducted, with the exception of the calculation of 95% CIs.

Analysis of key secondary endpoint 5: The extent of change in psychological impact (emotional and social functioning, and concerns relating to glabellar lines) at week 4 after the first treatment, in the BoNT/A-DP group in comparison with placebo, relative to baseline, as assessed by the modified Skindex-16 (GL-QoL) and the FACE-Q Appraisal of Lines Between Eyebrows and FACE-Q Age Appraisal VAS.

The modified Skindex-16 (GL-QoL) and FACE-Q Appraisal of Lines Between Eyebrows scale and FACE-Q Age Appraisal VAS scales will be analyzed according to the foreseen analysis approach of these tools, as described below.

Statistical Analysis Plan (SAP)

Emotional and Social Functioning

The modified Skindex-16 (GL-QoL) Emotional and Functioning domain and overall scores will be derived in accordance with the Skindex-16 manual, adapted for the GL-QoL. The scores will be standardized on a scale from 0 (no impact) to 100 (maximal impact); a scale score is the average of responses to items addressing a construct. Domain and overall scores will be calculated if at least two of each of three domain items are present. The absolute change from baseline (measured on the screening visit) will be calculated for the domain and overall scores and statistically compared between the treatment groups using the Wilcoxon Rank Sum test or t-test, if appropriate. Estimates of 'mild', 'moderate', and 'severe' psychological impact, and of the minimal clinical important difference, will be used to aid interpretation of scores and will be considered exploratory.

The analysis will be conducted with respect to the hierarchical order of key secondary endpoints; the analysis using the Emotional domain first, the Functioning domain second, and the overall score third. All analyses will be conducted on observed values only, i.e. missing domain and overall scores will be excluded from analysis; no imputation of missing domain and overall scores will be performed.

Concerns Relating to Glabellar Lines

The FACE-Q Appraisal of Lines Between Eyebrows scale and FACE-Q Age Appraisal VAS scores will be derived in accordance with the developers' instructions and missing data treated accordingly. The absolute change from baseline measured on the screening visit will be calculated for the FACE-Q Appraisal of Lines Between Eyebrows scale and for the FACE-Q Age Appraisal VAS score and statistically compared between the treatment groups using the Wilcoxon Rank Sum test. All analyses will be conducted on observed values only, i.e. missing scale scores will be excluded from analysis; no imputation of missing scores will be performed. This analysis will be conducted with respect to the hierarchical order of key secondary endpoints as well; the analysis of FACE-Q Appraisal of Lines Between Eyebrows scale first, followed by the analysis of FACE-Q Age Appraisal VAS scores.

Exploratory Analyses

Exploratory analyses of modified Skindex-16 (GL-QoL) domain and overall score and FACE-Q Appraisal of Lines Between Eyebrows scale and FACE-Q Age Appraisal VAS will also be conducted using the MFAS and the PP population. The analyses described in the two previous sections will be repeated for these populations.

Statistical Analysis Plan (SAP)

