12.4.2 Secondary Outcome Measures

Key Secondary Analyses:

The testing of the 5 key secondary endpoints will be performed with appropriate multiplicity control based on the FAS population. The results of each test result will only be considered confirmatory if the previous test in the order showed a confirmatory result at a one-sided significance level of 0.025. If the one-sided p-value is larger than 0.025 for any of the tests, the results of the subsequent tests will only be considered exploratory, and not confirmatory. The application of this hierarchical approach keeps the global significance level to 0.025 one-sided and requires no further adjustment of the significance level.

The following order of tests will be defined:

- Primary endpoint (composite endpoint)
- Key secondary endpoint 1
- Key secondary endpoint 2
- Key secondary endpoint 3
 - 3.1: The investigator's in-clinic assessments
 - 3.2: The subject's in-clinic assessments
- Key secondary endpoint 4
- Key secondary endpoint 5
 - 5.1: The modified Skindex-16 (GL-QoL) Emotional domain
 - 5.2: The modified Skindex-16 (GL-QoL) Functioning domain

Analysis of key secondary endpoint 1: The percentage of responders at maximum frown (as defined above) at week 12 (after the first treatment with BoNT/A-DP or placebo).

The same analyses, inclusive of the additional exploratory analyses, as described for the primary endpoint will be conducted.

Analysis of key secondary endpoint 2: The percentage of responders at week 16 (after the first treatment).

The analysis of the week 16 visit will be conducted on observed values only, i.e. missing investigator or the subject in-clinic assessments with the FWS at baseline or week 16 visit will be excluded from analysis but not assigned as being non-responders. Subjects who were re-treated before visit week 16 are considered to be non-responders.

In addition, the same analyses, inclusive of the additional exploratory analyses, as described for the primary endpoint will be conducted.

Analysis of key secondary endpoint 3: The proportion of subjects with a > 1 point reduction in FWS score at rest at week 4 in the first treatment cycle, based separately on the investigator and the subject in-clinic assessments

In general, the same statistical analyses, inclusive of the additional exploratory analyses as described for the primary endpoint, will be conducted.

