7.2 Handling of missing data

7.2.1 Missing data analysis methods

Analyses will be performed by visit. For responder analyses on visits at week 4 and week 12, missing in-clinic assessments (investigator or the subject) with the FWS at baseline or week 4 and week 12 visits will be assigned as being non-responders.

As sensitivity analyses, the following additional approaches for handling of missing values will be applied:

- Analysis on observed values only, i.e. missing values will be excluded from analysis.
- Last observation carried forward (LOCF)
- Tipping point analysis: each missing value will be assigned to either a response or non-response, so that all possible combinations of replacing one or more missing

Statistical Analysis Plan (SAP)

values within each treatment group will be analyzed. p-values will be calculated for each combination and graphically displayed using a scatter plot.

The analysis of the week 16 visit regarding the endpoint ‘percentage of responders at week 16 (after first treatment)’ will be conducted on observed values only, i.e. missing investigator or the subject in-clinic assessments with the FWS at baseline or week 16 visit will be excluded from analysis but not assigned as being non-responders. The same approach holds for the endpoint ‘percentage of responders at week 20 or later (after first treatment)’ respectively.

All analyses of the modified Skindex-16 (GL-QoL) Emotional and Functioning domain and overall scores will be conducted on observed values only, i.e. missing domain and overall scores will be excluded from analysis; no imputation of missing domain and overall scores will be performed. The same approach will be followed for the analyses of the FACE-Q scales.

The analysis of “responder” 4 weeks after re-treatment will be conducted on observed values only, i.e. subjects with missing investigator or the subject in-clinic assessments on FWS week 4 or at the preceding end of the cycle visit will be excluded from analysis.

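### In the confirmatory week 16 and week 20 responder tests, a documented relapser who declines re-treatment is dropped, while an identical relapser who accepts counts as a failure

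*SAP*

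**What the plan says.** Key secondary endpoints 2 and 4 are the composite responder rates at week 16 and at week 20 or later in cycle 1. Both stand in the fixed testing order at one-sided 0.025 (SAP 8.6.1.1).

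- **Week 16.** Protocol 12.4.2 states: "The analysis of the week 16 visit will be conducted on observed values only". SAP 8.6.3 repeats this and adds the rule for re-treated subjects: missing assessments "will be excluded from analysis but not assigned as being non-responders. Subjects who were re-treated before visit week 16 are considered to be non-responders".
- **Week 20.** "The analysis of visit week 20 will be conducted on observed values only", again with subjects re-treated before the visit counted as non-responders (SAP 8.6.3 and protocol 12.4.2).
- **Weeks 4 and 12.** The rule is different: missing FWS assessments at baseline or at the "week 4 and week 12 visits will be assigned as being non-responders" (SAP 7.2.1).
- **Other versions of endpoints 2 and 4.** The analyses "as described for the primary endpoint will be conducted as exploratory analyses" (SAP 8.6.3, endpoint 2; endpoint 4 is worded similarly). These bring in missing = non-responder, LOCF and tipping point.
- **Hierarchy sentence.** For endpoints 2 to 4, "the p-value to be considered within the hierarchical testing procedure is the one resulting from the Cochran-Mantel-Haenszel test" described in the Primary Analysis block of SAP 8.6.2.
- **Withdrawal.** A subject who does not agree to re-treatment is withdrawn and has the End of Study visit as early as possible (protocol 6.3.2, SAP 3.3). If the decision is made at a site visit, the End of Study procedures are done at that visit (protocol Table 9-1, footnote 10).

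**The concern.** A cycle ends only when investigator and subject both rate maximum frown at FWS 2 or more. A responder needs 0 or 1 from both, so a subject at that point is a documented failure. From there the two branches are treated differently:

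| Ratings at week 12 | Subject's decision | Week 16 and 20 status |
|---|---|---|
| FWS 2 or more by both raters | accepts re-treatment | non-responder, in the denominator |
| FWS 2 or more by both raters | declines, is withdrawn | missing, out of the denominator |

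Willingness to be injected again is not an efficacy outcome, yet it decides how the same relapse is classified. Endpoints 2 and 4 carry the confirmatory evidence on duration of effect. What is at stake is the reported late response rate and, if decline rates differ between arms, the confirmatory p-value.

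**Working it through.** **1. The plan's own figures.** The documents give no power or sample size for week 16 or week 20. The week 4 calculation reproduces: exact one-sided Fisher power at 60% v 10% is 91.6% for 42/14 and 89.3% for 39/13. The stated half-width of about 4.5% also reproduces: 1.96 × √(0.60 × 0.40/450) = 4.53%. Neither figure depends on the rule discussed here.

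**2. Who is affected.** Week 16 loses those who relapse and decline at week 12. Week 20 loses those who decline at week 12 or week 16. A subject who first relapses at week 16 and then declines is still observed at week 16. A subject with both ratings at 2 or more who is deferred for another reason, such as local infection, may return 4 weeks later and is not affected in the same way.

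**3. Effect on one arm.** Let p be the response rate with all documented relapsers counted as failures, and m the share of the arm dropped. Assuming that relapsers do not regain response untreated, the observed-only rate is p/(1-m). For p = 20%:

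| m | Calculation | Observed-only rate |
|---|---|---|
| 1% | 0.20/0.99 | 20.2% |
| 2% | 0.20/0.98 | 20.4% |
| 5% | 0.20/0.95 | 21.1% |
| 10% | 0.20/0.90 | 22.2% |

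**4. Effect on the difference at week 16 (all inputs assumed).** Take true rates of 20% v 2%, a difference of 18.0 points, on 525 v 175 subjects. Let e be the share relapsed at week 12 and d the share of those who decline, so m = e × d. With e = 60% active and 98% placebo:

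| d | m, active / placebo | Dropped, active / placebo | Rates | Difference |
|---|---|---|---|---|
| 2% | 1.2% / 2.0% | 6 / 3 | 20.2% v 2.0% | 18.2 |
| 5% | 3.0% / 4.9% | 16 / 9 | 20.6% v 2.1% | 18.5 |
| 10% | 6.0% / 9.8% | 32 / 17 | 21.3% v 2.2% | 19.1 |

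With e = 40% and 95%, the differences are 18.1, 18.3 and 18.6.

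**5. Type I error.** Simulated site-stratified CMH test: 18 sites, 525 v 175, both arms 20%, one-sided 0.025, known failures removed at random within arm.

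| Loss, active / placebo | Type I error |
|---|---|
| none | 0.023 |
| 2%, 5% or 10% in both arms | 0.022 to 0.023 |
| 5% / 3% | 0.030 |
| 3% / 5% | 0.017 |

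**6. Power for a small late effect.** At 8% v 2% with e = 60% and 98%, power is 87.6% under observed-only and 88.8% with decliners counted as failures at d = 5%; at d = 10% it is 86.1% v 88.8%. Observed-only can therefore also cost power.

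**7. Which rule feeds the hierarchy.** The Primary Analysis block in SAP 8.6.2 contains a missing-data sentence: subjects with missing assessments "at baseline or visit week 4 will be assigned as being non-responders". That sentence is worded for week 4. SAP 7.2.1 confines missing = non-responder to weeks 4 and 12 and prescribes observed values for weeks 16 and 20. SAP 8.6.3 and protocol 12.4.2 agree, and SAP 8.6.3 makes the primary-style versions exploratory. The hierarchy sentence names the CMH test from the first paragraph of the block. Observed-only is the better reading. The wording is still loose: one pointer covers endpoints with opposite missing-data rules, and only endpoint 3 ties its rule to the hierarchy ("For the primary analysis (to be considered within the hierarchical testing procedure), subjects with missing investigator in-clinic assessments").

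**The case against.** The strongest reply has three parts.

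**The effect is small and undocumented.** Decline rates, relapse rates and late response rates are all assumed. Equal loss leaves type I error alone. The 0.030 case needs more loss in the active arm, whereas in step 4 placebo loses the larger share. Under a true null with blinded arms, similar loss would be expected. This stands and limits the weight of the point. It does not justify classifying the same relapse in two ways.

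**The alternatives are already planned.** Missing = non-responder, LOCF and tipping-point analyses would reveal any divergence. That is correct, but they are exploratory and do not supply the confirmatory p-value.

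**The rules do not conflict.** A reader might infer that the SAP sets two contradictory missing-data rules for these tests and leaves the analyst to choose after unblinding. The documents do not support that, for the reasons in step 7. Only a clarification of the pointer is needed.

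A reader might also take the 10% drop-out in SAP 5 as a ceiling on m. It is a planning assumption for the whole study and does not bound the loss in either arm.

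**Conclusion.** The inconsistency is real on the text: under the confirmatory rule for weeks 16 and 20, a documented relapser is a failure or is excluded depending on whether re-treatment is accepted. Within an arm the exclusion can only raise the reported rate, by the factor 1/(1-m), provided relapsers do not regain response untreated. The size is unknown because m is not documented. In the week 16 illustration, with 2% to 10% declining, the difference moves by 0.1 to 1.1 points.

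The documents do not support a claim that the treatment effect is overstated or that type I error is inflated. The direction depends on how loss splits between arms. With a large late effect the test conclusion is unlikely to change. The week 4 primary analysis is not touched. The point covers documented relapsers only, not drop-outs for other reasons. It is an inexpensive improvement to a confirmatory analysis and should be made.

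**What to change.** - **Rule.** In the confirmatory week 16 and week 20 tests, count as a non-responder any subject who, at a cycle 1 Evaluation for Re-treatment visit (week 12 or later) before the analysed visit, was rated FWS 2 or more at maximum frown by both raters and whose cycle 1 ended there, by re-treatment or by withdrawal. The tie to that visit is essential, because every subject meets the FWS condition at baseline.
- **Alternative.** Make the already planned FAS missing = non-responder analysis confirmatory, as at weeks 4 and 12. It is simpler, but it also counts drop-outs for other reasons as failures.
- **Clarification.** Say in SAP 8.6.3 that the hierarchy sentence imports the CMH test and site strata only, and name the missing-data rule that feeds the hierarchy for endpoints 2 and 4, as is done for endpoint 3.
- **Sensitivity.** Keep observed-only, LOCF and tipping point.

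Cost: no new data, a short text change in SAP 8.6.3 and one derivation rule. Because protocol 12.4.2 states the observed-only rule, the change must be listed in SAP section 9 and documented before unblinding. Late response rates become slightly less favourable.
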